Models to Arrange Long-Term Employment-Based Abstinence Reinforcement

We developed three models to maintain employment-based abstinence reinforcement ([name], Holtyn and Morrison, in press; Appendix). Under all models, individuals enroll in Phase 1 to initiate abstinence and establish skills. The models differ in how employment-based reinforcement is maintained.

The Social Business Model. Under the Social Business model, Phase 1 graduates are hired as employees in a social business. A social business, a concept that won Muhammad Yunus the Nobel Prize, exists to address the needs of low-income people (Weber & Yunus, 2010; Yunus & Weber, 2007). We established a Therapeutic Workplace Social Business, Hopkins Data Services, to maintain employment-based abstinence reinforcement. Our experience suggests that the Therapeutic Workplace Social Business can be feasible ([name] et al., 2005) and effective (Aklin et al., 2014), but it may have limited capacity and is difficult to scale up relative to our other models.

The Cooperative Employer Model. Under the Cooperative Employer model, a community employer hires Phase 1 graduates and requires that they undergo drug testing and remain abstinent to maintain employment. This model is more scalable, but has limited capacity, since it requires cooperating employers.

The Wage Supplement Model. Under the Wage Supplement Model, graduates of Phase 1 are offered abstinence-contingent wage supplements if they maintain employment. Governments in Minnesota, Connecticut, Milwaukee, New York, and Canada have used wage supplements to increase employment in welfare recipients (Berlin, 2007; Michalopoulos, 2005; Riccio et al., 2010). This model harnesses the power of wage supplements to promote employment, while simultaneously using the wage supplements to reinforce alcohol abstinence. We have used abstinence-contingent wage supplements in occasional participants who obtain employment while participating in the Therapeutic Workplace ([name] et al., 2002).

Development and Evaluation of the Abstinence-Contingent Wage Supplement Model

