Verification of employment. To gain verified and objective records of employment, we may get an objective measure of each participant's employment history by getting each participant's earnings history using federal Form SSA-7050-F4 (10-2016) UF, REQUEST FOR SOCIAL SECURITY EARNINGS INFORMATION. Participants and research staff will complete this form and have the participant's earnings history sent to our research unit. Our research unit will pay for the costs of this service. We may request these documents one or more times. We will take the following steps to protect this sensitive information in our study databases: (1) when storing a completed form, we will redact name, date of birth, and social security number from the written document and label the document with an ID number; (2) keep paper copies in a locked file cabinet in a locked office and never keep documents out while unattended by research staff; and (3) only enter relevant information into the database (i.e., information about when participants worked, how much they earned, and what type of employment they had). The risks associated with collecting this information are explained on the consent form.

b. Study duration and number of study visits required of research participants.

Participants will be invited to enroll in Phase 1 of the therapeutic workplace for 1 month. All participants that report to be assessed at the end of Phase 1 and are willing to continue to wear a wearable alcohol biosensor will be randomly assigned to the study groups and followed for 6 months. All participants will be invited to participate in an intake assessment to determine eligibility and characterize the population. Outcome assessments will be conducted immediately prior to random assignment, every 30 days throughout the 6-month intervention evaluation period after random assignment and then at 6 and 12 months after the end of the intervention evaluation period. These assessments may be collected using REDCap and conducted via phone or web-conferencing.

NA

c. Blinding, including justification for blinding or not blinding the trial, if applicable.

NA

d. Justification of why participants will not receive routine care or will have current therapy stopped.

NA

e. Justification for inclusion of a placebo or non-treatment group.

NA

f. Definition of treatment failure or participant removal criteria.

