Participants will be removed from the study if they threaten the safety of CLH staff or other research participants, or of any other persons on the Johns Hopkins Bayview Campus.

g. Description of what happens to participants receiving therapy when study ends or if a participant's participation in the study ends prematurely.

Throughout the study, participants will be given referrals to services they might need (e.g., drug counseling, housing, medical, or employment services).

5. Inclusion/Exclusion Criteria

Inclusion criteria: a) 18 to 55 years old; b) homeless at the time of intake as defined by the McKinney-Vento Homeless Assistance Act (lacked a fixed, regular, and adequate nighttime residence including staying in a shelter, on the street, in an abandoned house or building, a car, or a park); c) unemployed; d) meet DSM V criteria for alcohol use disorder; and e) interested in obtaining employment. Exclusion criteria: a) report current suicidal/homicidal ideation; b) currently have nickel or other metal allergies, deep vein thrombosis, or leg ulcers where the SCRAM bracelet should be placed. Individuals excluded from the study will be linked with appropriate care as needed.

6. Drugs/ Substances/ Devices

NA a. The rationale for choosing the drug and dose or for choosing the device to be used.

NA b. Justification and safety information if FDA approved drugs will be administered for non-FDA approved indications or if doses or routes of administration or participant populations are changed.

NA c. Justification and safety information if non-FDA approved drugs without an IND will be administered.

NA

7. Study Statistics

a. Primary outcome variable.

Biologically-Verified Alcohol Abstinence (primary aim). Assess the effectiveness of *IPS Plus Abstinence-Contingent Wage Supplements* in promoting biologically-verified alcohol abstinence during the intervention. We will assess the number of days of alcohol abstinence (based on transdermal alcohol concentrations) during the 6 months after random assignment. Primary Hypothesis: Our primary hypothesis is that *IPS Plus Abstinence-Contingent Wage Supplements* will promote alcohol abstinence during the intervention after random assignment relative to Usual Care Control.

b. Secondary outcome variables.

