Self-Reported Alcohol Use (secondary aim). Assess the effectiveness of *IPS Plus Abstinence-Contingent Wage Supplements* in reducing self-reported alcohol use during the intervention. We will use three self-report measures of alcohol use (based on TLFB) during the 30 days prior to each of the 6 monthly assessments during the year after random assignment. We will assess: 1) the percent of days abstinent from alcohol; 2) the average number of standard drinks per drinking day ingested; and 3) the percent of heavy drinking days (≥ 5 standard drinks per day for men and ≥ 4 standard drinks per day for women). Hypothesis: We expect that *IPS Plus Abstinence-Contingent Wage Supplement* participants will have less self-reported alcohol use during the intervention after random assignment relative to Usual Care Control.

Employment (secondary aim). Assess the effectiveness of *IPS Plus Abstinence-Contingent Wage Supplements* in promoting employment during the intervention. We will assess the number of days participants are employed during the 30 days prior to each of the 6 monthly assessments during the intervention after random assignment. Hypothesis: We expect that *IPS Plus Abstinence-Contingent Wage Supplements* will increase employment during the intervention after random assignment relative to Usual Care Control.

Post-Intervention Effects (secondary aim). Assess the effectiveness of IPS Plus Abstinence-Contingent Wage Supplements in promoting employment and abstinence from alcohol after the intervention ends. We will compare the groups on self-reported measures of alcohol use and employment at 6- and 12-month follow-up assessment time points after the intervention ends. Hypothesis: We expect that IPS Plus Abstinence-Contingent Wage Supplements may need to be maintained to promote long-term employment and abstinence from alcohol, and thus alcohol abstinence and employment may not be sustained after the intervention ends.

Economic Outcome Measures

Costs of Treatment (secondary aim). Assess the costs of treatment for Usual Care and IPS Plus Abstinence-Contingent Wage Supplements. We will assess the total cost per participant in both study groups. Hypothesis: We expect that treatment costs for IPS Plus Abstinence-Contingent Wage Supplements will be higher per person relative to Usual Care due to the IPS and wage supplements and because we expect that IPS Plus Abstinence-Wage Supplement participants will have greater treatment engagement.

[figure not shown]

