regression and GEE will be expressed using odds ratios with 95% CI. Analyses will include all randomized participants as intent-to-treat, and will be adjusted for pre-specified covariates used for stratification (Pocock et al., 2002). Tests will be two-sided and, because we have one primary outcome, alpha will be set at 0.05. Based on our previous experience, we expect rates of attrition at monthly visits to be low. If rates are higher than expected, we will use mixed effects models rather than GEE estimation, as the former has less strict assumptions regarding missing data (MAR, rather than MCAR). If it appears that the missing data are MNAR, then we will fit pattern mixture models as described by Hedeker & Gibbons (1997).

Missing data. We expect to collect >90% of assessments. Our approach to handle missing data will be to impute all missing values as the adverse outcome (e.g., alcohol positive). Model parameter estimates from this approach will be compared to a method without imputation. If these methods yield differing results, conclusions will need to be tentative, but results from both approaches will be reported in publications. To investigate sensitivity to missing values, participants with and without missing values will be compared by covariates and treatment assignment. If rates of missingness are higher than expected, we may use multiple imputation (Rubin, 1996) or pattern mixture models (Hedeker & Gibbons, 1997) to obtain unbiased estimates of treatment effects.

Consideration Of Sex And Other Variables In Moderating The Outcomes

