There are risks that the confidential information we collect could be revealed to people not involved in the research such as a friend, relative, or an outside organization. This could be embarrassing to the participant if the participant wanted to keep participation in the study secret. The legal risks are limited because we collect only general information about participant activities, legal and illegal. We do not collect information about specific illegal acts. Thus, the risks associated with the assessments are not greater than the risks associated with routine psychological examinations or tests.

e. Financial risks to the participants.

There are no financial risks above those of normal daily living. Each participant is responsible for ensuring that the earning of incentives is reported properly to relevant government or private agencies and for determining whether or not the earnings will affect any benefits they might receive from those agencies.

9. Benefits

a. Description of the probable benefits for the participant and for society.

Benefits for the participant. All participants will have access to training in skills that could be useful in obtaining employment. Training will be provided in typing, keypad, general computer use, reading, math, GED preparation, and the use of Microsoft computer applications. IPS supported employment will be provided to help participants become employed. Since all participants in this study will be unemployed at the start of the study, this experience could help prepare participants for employment.

All participants will receive monetary incentives for participating in the Therapeutic Workplace during the first month of the study. Participants in the IPS Plus Abstinence-Contingent Wage Supplements group will get abstinence-contingent incentives for engaging in IPS supported employment and for obtaining and maintaining competitive employment. These incentives should increase participation in the Therapeutic Workplace, development of job skills, employment, and abstinence from alcohol. The earnings and payments could also have the benefit of providing a means of purchasing things that the individual would not otherwise be able to afford, including housing.

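### Unemployment is required at intake but not re-applied at randomization, and the employment models leave out pre-randomization employment: a small, avoidable loss of precision on a secondary outcome

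*Combined protocol and SAP*

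**What the plan says.** - **Entry.** Section 5 lists "c) unemployed; d) meet DSM V criteria for alcohol use disorder". The unemployment criterion carries no date of its own. Section 4.b describes an "intake assessment to determine eligibility and characterize the population", and section 9.a says "Since all participants in this study will be unemployed at the start of the study". I therefore read unemployment as judged at intake.
- **Randomization.** Phase 1 lasts about one month: one week of induction and three weeks of paid job-skills training (section 4.a). Under section 4.b, those who attend the end-of-Phase-1 assessment and will keep wearing the biosensor are randomized. Employment is not a condition at that point.
- **Jobs during the Therapeutic Workplace.** Section 3 says of earlier work: "We have used abstinence-contingent wage supplements in occasional participants who obtain employment while participating in the Therapeutic Workplace".
- **Baseline measurement.** "Outcome assessments will be conducted immediately prior to random assignment" (section 4.b).
- **Outcome.** "We will assess the number of days participants are employed during the 30 days prior to each of the 6 monthly assessments" (section 7.b). Self-reported employment is compared again 6 and 12 months after the intervention ends.
- **Model.** Section 7.c says the analyses "will be adjusted for pre-specified covariates used for stratification". Section 4.a names these: abstinent days before randomization, opiate and cocaine use, high school or GED, and gender. Pre-randomization employment is also absent from the moderators in section 7.c.

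**The concern.** Employment during the intervention is a stated secondary aim, and whether someone already has a job at randomization is likely to predict later days worked strongly. The plan accepts this logic elsewhere. It stratifies on and adjusts for pre-randomization abstinence because that should predict abstinence later, and it includes schooling because that should be associated with employment. For the employment outcome it uses the schooling proxy but not earlier employment itself.

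If everyone were still unemployed at randomization, nothing would be missing. But the criterion applies a month earlier, to people who want work and are in paid job training. At stake are the width of the confidence interval for the employment effect and how far a chance difference in job-holders between arms can move the estimate.

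**Working it through.** **The plan's own figure.** Section 7.c states no power for employment. Its sample size concerns the primary abstinence outcome: 130 × 0.90 = 117, which is exact and does not change here.

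**Inputs.** From the documents: 130 randomized. Assumed: 65 per arm (equal allocation is not stated) and the share *p* employed at randomization, which the documents do not give, taken as 2% to 15%. Also assumed: job-holders work 55% of days in both arms; others work 15% (control) or 27% (intervention).

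**1. Chance imbalance.** The SD of the between-arm difference in the share employed is √(2p(1−p)/65):
- 5%: √(2 × 0.05 × 0.95/65) = 3.8 percentage points
- 10%: √(2 × 0.10 × 0.90/65) = 5.3 points
- 15%: √(2 × 0.15 × 0.85/65) = 6.3 points

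Job-holders work 40 points more than others in control (55 − 15) and 28 more in intervention (55 − 27), an average of 34. A one-SD imbalance then moves the unadjusted difference by about 3.8 × 0.34 = 1.3, 5.3 × 0.34 = 1.8 and 6.3 × 0.34 = 2.1 points. The assumed effect among those not yet employed is 27 − 15 = 12 points.

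**2. Precision.** Simulation of 4,000 trials per scenario. Each person's share of days worked is drawn from a beta distribution with the means above and concentration 1.5. A linear model is fitted with and without employed Y/N at randomization. The SE reduction is 1 − √(variance ratio).

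| Employed at randomization | Variance ratio, adjusted/unadjusted | SE reduction |
|---|---|---|
| 5% | 0.925 | 3.8% |
| 10% | 0.882 | 6.1% |
| 15% | 0.843 | 8.2% |

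At 2% the SE falls by about 2%. The probability that at least one arm then has no job-holder is 1 − (1 − 0.98^65)² = 1 − (1 − 0.269)² = 0.47, so the covariate would often carry almost no information.

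**3. Sensitivity to the assumed gap.** With between-person SD 0.35, the variance explained is R² = p(1−p) × gap²/0.35², and the SE falls by 1 − √(1 − R²):
- Gap of 30 points: 0.7% at p = 2%, 1.8% at 5%, 4.8% at 15%.
- Gap of 50 points: 2.0% at p = 2%, 5.0% at 5%, 14% at 15%.

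**4. Closer to the planned model.** A binomial logit with robust SEs, on one summary per person and with the work rates of step 2, gave power without and with the covariate of 70% and 72% (p = 2%), 65% and 69% (5%), 58% and 65% (10%), 49% and 58% (15%). Compare within each pair only. Power falls across the pairs partly because job-holders are assumed to gain nothing from the intervention.

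**5. Validity.** In a separate simulation (50-point gap; 5%, 10% and 20% employed), the unadjusted linear analysis averaged 0.149 to 0.150 for a true difference of 0.15. With no true difference it rejected in 4.7% to 4.9% of trials.

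**The case against.** The strongest reply is that nothing is invalid. Randomization comes after Phase 1, so a job found in Phase 1 is a baseline characteristic, balanced in expectation. That stands, and step 5 agrees.

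The premise is also thin. Section 3 speaks only of occasional participants in earlier work, without a rate. Phase 1 is short, and supported employment starts only afterwards. Section 3 puts full-time work at about 20% even after Therapeutic Workplace participation. The true share at randomization may be near zero. That stands too, and it is why the size is given as a range. The calculation is simpler than the planned repeated-measures GEE and omits the four planned covariates; schooling may already capture part of the effect.

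A reader might infer that counting days in a job found before randomization contaminates the outcome. The documents do not support this. The outcome is days employed, not jobs found, and sections 3 and 4.a pay supplements for keeping and working in a job. Days kept in an earlier job are a legitimate target.

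A reader might also extend the point to housing, since section 5 requires participants to be "homeless at the time of intake as defined by the McKinney-Vento Homeless Assistance Act". Homelessness enters as a cost-effectiveness outcome. Section 7.c describes that analysis as a ratio of differences with bootstrap intervals and sets out no homelessness regression to which a covariate could be added. Nothing in the documents lets a size be put on it, so it is not part of this point.

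**Conclusion.** The point holds as a minor matter of efficiency and reporting. Participants employed by the end of Phase 1 can be randomized, and the employment models do not use that information although an assessment is made at the right time. The SE reduction is roughly 4% at 5% employed and 8% at 15%, and little or nothing if almost nobody is employed. All of this rests on assumed shares and work rates. A claim of bias or inflated type I error would go too far. The primary analysis and the sample size are untouched.

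**What to change.** In section 7.c, prespecify pre-randomization employment as an added covariate in the employment models for both the intervention and follow-up periods. Use days employed at the pre-randomization assessment or employed Y/N, and choose one before the arms are compared. The 30-day window is stated only for the six later assessments, so say that the same window and definition of employment apply at the earlier one. Days worked may understate a job begun late in Phase 1, which is an argument for Y/N. Report employment status at randomization by arm, so that readers can see how many participants were keeping a job rather than finding one.

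The cost is a sentence or two, with no change to entry or sample size. No new data are needed provided the pre-randomization assessment records employment, as its description as an outcome assessment implies. There are two drawbacks: the covariate may have few non-zero values, and the odds ratio becomes conditional on it, so it will not be numerically comparable with one from a model without it.

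### After a missed monthly interview, the plan provides no look-back for self-reported drinking or days employed, and its stated approach scores the missed window as adverse

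*Combined protocol and SAP*

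**What the plan says.** Section 7.b defines three drinking measures from the timeline follow-back (TLFB) calendar (percent of days abstinent, drinks per drinking day, percent of heavy drinking days) "during the 30 days prior to each of the 6 monthly assessments during the year after random assignment". For employment, the outcome is the "number of days participants are employed during the 30 days prior to each of the 6 monthly assessments". Section 4.b schedules these assessments "every 30 days throughout the 6-month intervention evaluation period after random assignment", so six of them span 6 × 30 = 180 days. The drinking text speaks of a year and section 4.b of six months. The two should be reconciled; I take six months.

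Section 4.b adds: "These assessments may be collected using REDCap and conducted via phone or web-conferencing". No section gives a visit window, a rule for late interviews, or a longer look-back after a missed one.

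On missing values, section 7.c says: "Our approach to handle missing data will be to impute all missing values as the adverse outcome (e.g., alcohol positive"). It continues: "Model parameter estimates from this approach will be compared to a method without imputation". Both results will be published, and conclusions are called tentative if they differ. Multiple imputation or pattern mixture models are optional if missingness exceeds expectation. The plan expects to collect more than 90% of assessments.

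**The concern.** Both instruments ask about individual past days, so a participant who misses interview 2 and attends interview 3 could still be asked about days 31 to 60. The outcome definition does not use that opportunity. Followed as written, it leaves those days outside every window and replaces them with an assumed adverse value in the stated approach.

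Two effects on the secondary outcomes follow, and they should be kept apart. With equal missingness in both arms, adverse scoring shrinks a true difference. With unequal missingness, it can create or distort one. Unequal completion is plausible but not established: section 4.a has intervention participants engaging in about four hours of supported employment each weekday, and section 7.b expects greater treatment engagement in that arm. The documents give no completion rates by arm.

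**Working it through.** **Inputs from the plan.** 130 randomized; 10% missing (7.c, Power Analysis); six interviews 30 days apart (4.b); 30-day windows (7.b); missing scored as adverse (7.c). The 15-point difference comes from the power analysis for the primary outcome and is borrowed here, because the plan gives no effect size for these outcomes.

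**The plan's own figure.** 130 × 0.90 = 117, as stated.

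**What is lost without catch-up.** 130 × 6 = 780 windows; 10% is 78 windows, or 18 of 180 days per participant on average. One missed interview leaves 30/180 = 16.7% of a participant's days unobserved.

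**Missing windows after catch-up**, with misses assumed independent at rate d:

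- Next interview only. Each of windows 1 to 5 stays missing only if the next interview is missed too, and window 6 has no later monthly interview: (5d² + d)/6. At d = 0.10, (0.05 + 0.10)/6 = 2.5%, so 75% are recovered.
- Any later monthly interview: (d + d² + … + d⁶)/6. At d = 0.10, 0.111111/6 = 1.85%, so 81.5% are recovered.

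| Assumed d | Next interview only | Any later monthly interview |
|---|---|---|
| 5% | 1.0% | 0.9% |
| 10% | 2.5% | 1.85% |
| 20% | 6.7% | 4.2% |
| 30% | 12.5% | 7.1% |

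If every missing window comes from permanent dropout, the recovery is zero.

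**Equal missingness, true difference 15 points.** Observed difference = 15 × (1 − m), where m is the proportion of windows still missing.

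- No catch-up: 15 × 0.90 = 13.5
- Next interview: 15 × 0.975 = 14.6
- Any later monthly interview: 15 × 0.9815 = 14.7

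**Unequal missingness, no true difference, 50% in both arms (assumed).** Spurious difference = 0.50 × (m_control − m_intervention).

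- 15% v 5%: 0.50 × 0.10 = 5.0 points. With next-interview catch-up the missing shares become 4.375% and 1.042%, giving 1.7 points.
- 12% v 8%: 2.0 points, falling to 0.7.
- 5% v 15%: the same sizes with the sign reversed, −5.0 and −1.7.

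**Late interviews.** An interview L days late still returns a full 30-day value. It leaves L days in no window, and counts L days twice if the next interview is on schedule: 7 days is 3.9% of 180 and 14 days is 7.8%. None of the figures above comes from lateness.

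**The case against.** The strongest reply is that section 7.b defines what is analysed and does not forbid asking further back. A reader might infer that missed days are barred from later interviews and lost for good; the text does not say so. Employment might also be recovered from the Social Security earnings history (4.a) or the modified Economic Form 90 (7.c), although the first is optional and neither is tied to the days-employed outcome. This stands against the stronger reading. It does not supply a rule, and interviewers need one.

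A reader might also infer that controls are out of contact and that bias between arms is therefore likely. The documents do not support that. Controls are paid to wear the biosensor for six months (4.a), up to $11 per day, and both arms receive $30 per monthly assessment (10.a). SCRAM wearers come in about every 30 days (4.a). The unequal-missingness figures are scenarios.

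The plan's safeguards count too. The comparison without imputation would expose sensitivity to adverse scoring, and participants with and without missing values are to be compared by treatment assignment. But these diagnose the problem and return no data. Section 7.c itself links GEE to the assumption that data are missing completely at random.

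Finally, uniform 30-day recall is a defensible choice, and catch-up may exchange unequal missingness for unequal recall length. Under 15% v 5%, next-interview catch-up would fill 15 − 4.375 = 10.6% of control windows and 5 − 1.042 = 4.0% of intervention windows from longer recall. That cost is real, but it can be reported and tested; an imputed adverse value carries no information about the days it replaces.

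**Conclusion.** The gap is real, and its consequences are limited. The plan states no look-back after a missed interview, and its stated approach scores the missed window as adverse. At the planned 10%, catch-up would leave 2.5% of windows missing (1.85% with any later monthly interview). This is a best case: it requires intermittent, independent misses, and it gives nothing for permanent dropout or for window 6. The illustrative gain under equal missingness is 1.1 to 1.2 points on a borrowed 15-point difference.

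Two further inferences should be resisted. Late interviews are not scored as adverse; they cause small gaps or overlaps in outcomes analysed per window, and no bias from them has been shown. The primary outcome and the sample size are also untouched, because the primary outcome comes from the biosensor. The adverse-scoring arithmetic cannot be applied to drinks per drinking day, for which the plan defines no adverse value. Minor priority.

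**What to change.** In section 7.b and in the assessment procedure:

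1. When an interview was missed, ask the TLFB calendar and days employed back to the last completed assessment.
2. Assign the answers to 30-day windows counted from randomization.
3. Impute only windows that no later monthly interview covers.
4. Report a sensitivity analysis limited to windows recalled within 30 days, and give the share of longer-recall windows by arm.

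The cost is a few more minutes for participants who missed an interview. No new visit or instrument is needed, and interviews may already be done remotely. The downside is recall beyond 30 days for recovered windows, possibly more often in one arm; step 4 is there to show whether that matters.
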